Across the completed phase 1 and 2a studies, there have been a small number of mild, transitory transaminase elevations observed both in patients/subjects who received either fezolinetant or placebo. There were no incidences of raised TBL and none of the patients/subjects experienced associated symptoms. In the recently completed phase 2b study ESN364_HF_205, transitory increases in transaminase enzymes, ALT/aspartate aminotransferase (AST), have been reported in 7 subjects between 4 and 8 weeks after start of study treatment and in 2 unique subjects during study follow-up. Subjects were reported to be asymptomatic throughout and there was no evidence of functional liver impairment. Although there were cases with evidence of significant underlying hepatic conditions and other confounding factors, independent expert review of the cases that met a stopping rule concluded that the study drug was probably the cause of the increased transaminase levels. In all cases, transaminase enzyme levels rapidly decreased, in 2 cases during continuing treatment with study medication.

Based on cases of increased AST and ALT > 5 × ULN in the phase 2b study ESN364_HF_205 that were assessed by external hepatic experts as related to the use of fezolinetant, liver injury has been categorized as an important potential risk. Monitoring of liver parameters is incorporated in the design of this protocol, including individual patient stopping rules and liver assessment per [[Section 12.5](#)]. Increased transaminases have not been observed at the dose selected for this study, i.e., 30 mg fezolinetant once daily [[Section 2.2.2 Dose Rationale](#)].

Severe thrombocytopenia has been reported in non-clinical studies but not in clinical studies and has been categorized as an important potential risk. To date, 1 clinical case of mild, pre-existing, thrombocytopenia has been reported (in phase 2a Study ESN364_HF_204). Platelet counts are included in the hematological monitoring during the course of the study.

Circumoral paresthesia has been reported by several subjects taking fezolinetant. Considering the reported cases in the phase 1 studies (ESN364-CPK-101 and ESN364-CPK-102) the occurrence of circumoral paresthesia is dose dependent for both intensity and duration,

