A relationship between fezolinetant exposure (dose and concentration) and the incidence of liver parameter elevations appears to be present. Individual predicted exposures for subjects with transaminase elevations $> 3 \times \text{ULN}$ were compared to the broader distribution of fezolinetant exposure by treatment group. Subjects with ALT or AST elevations $> 3 \times \text{ULN}$ generally had steady-state C_{max} and C_{avg} concentrations toward the higher end of the distribution for each dose group. Most cases of ALT or AST elevations $> 3 \times \text{ULN}$ occurred at fezolinetant exposures anticipated from 120 mg total daily doses or higher. Two subjects receiving a 60 mg total daily dose (1 in 30 mg bid and 1 in 60 mg qd) experienced ALT or AST elevations $> 3 \times \text{ULN}$. The subject in the 60 mg once daily dose group had an average concentration consistent with the 75% percentile of exposure for the 120 mg total daily dose. The transaminase elevation for the subject in the 30 mg twice daily group occurred at the follow-up visit, 3 weeks after the last dose. The subject had normal liver parameters throughout the study and the elevation was considered to be unlikely related to study drug.

Dose- and concentration-response models were developed to identify the minimum effective dose and the exposure-response relationship. Both the dose-response (Multiple Comparison Procedure – Modeling) and concentration-response (nonlinear mixed-effects models) analyses demonstrated increased improvements in HF frequency and HF severity with

increasing fezolinetant exposure. No clinically relevant difference was noted between predicted efficacy (frequency or severity) for the once daily and twice daily regimen given the same total daily dose.

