5 ENDPOINTS

5.1 Primary Safety Endpoint

The primary variable will require the evaluation of the effect of fezolinetant on the following:

- Frequency and severity of AEs.
- Percentage of subjects with endometrial hyperplasia.
- Percentage of subjects with endometrial cancer.

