6.5 Analysis of Safety

Overall long-term safety of fezolinetant and the effect of fezolinetant on endometrial health will be the primary objective of this study. The safety assessments include adverse events, laboratory assessments, vital signs, C-SSRS, ECG, endometrial health assessment and imaging (mammogram, DXA, TVU). In all analysis of safety, the treatment group includes placebo, fezolinetant 30mg, fezolinetant 45mg and fezolinetant total will be presented by treatment group for SAF, unless specified otherwise. For analyses by visit, the analysis windows from Section 6.10.1 will be applied. Except for adverse events and follow-up visit data, only data up to one day after the last dose date will be considered for the analyses.

The baseline value for safety endpoint will be the last non-missing value taken on or prior to first dose of study drug unless otherwise noted.

Primary Safety Variables

- Frequency and severity of AEs.
- Percentage of subjects with endometrial hyperplasia.
- Percentage of subjects with endometrial cancer.

Secondary Safety Variables

- Change from baseline in endometrial thickness at 12 months.
- Percentage of subjects with disordered proliferative endometrium.
- Change from baseline in bone mass density (BMD) and trabecular bone score (TBS) at hip and spine at 12 months.
- Change from baseline to each timepoint in vital signs: sitting systolic and diastolic blood pressure and pulse rate.

- Change from baseline to each timepoint in laboratory tests: hematology, biochemistry and urinalysis.
- C-SSRS at each timepoint.
- Change from baseline to each timepoint in ECG parameters

Exploratory Safety Variables

- Change from baseline to specified time points in serum concentrations of sex hormones and sex hormone-binding globulin (SHBG) (week 4, 12, 24, 52 and 55).
- Plasma concentration of fezolinetant and the fezolinetant metabolite ESN259564 at specified timepoints (week 4, 12, 24 and 52).

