6.5.1 Adverse Events

Per protocol, a treatment emergent adverse event (TEAE) is defined as the AEs that occurred on or after first dose of study drug and 21 days after the last dose of study drug (when AE collection closes).

A study drug-related TEAE is defined as any TEAE with a causal relationship of YES by the investigator.

The sponsor has a list of events that they classify as "always serious" events. If an AE is reported that is considered by the sponsor to be an SAE per this classification as "always serious", the AE will be treated as an SAE in tables and listings, and flagged as 'always serious' in AE listings.

An overview table will include the following

- Number of TEAEs,
- Number and percentage of subjects with TEAEs,
- Number of drug related TEAEs,
- Number and percentage of subjects with causally drug related TEAEs,
- Number of serious TEAEs,

- Number and percentage of subjects with serious TEAEs,
- Number of serious drug related TEAEs,
- Number and percentage of subjects with serious drug related TEAEs,
- Number of TEAEs leading to permanent discontinuation of study drug,
- Number and percentage of subjects with TEAEs leading to permanent discontinuation of study drug, and
- Number of deaths.

In order to adjust for differences in subjects' durations and the potential differential dropout rates between the treatment groups, an overview table to report exposure adjusted incidence rate (per 100 subject-years) for the above AE categories will be summarized. The total subject-years of exposure is calculated as the sum over subjects of the total duration of exposure divided by 365.25:

$$\sum_{i} \frac{ld_i - fd_i + 1}{365.25},$$

where fd_i and ld_i denote the first dose date of study drug and the last dose date of study drug for subject *i*.

The number and percentage of subjects with TEAEs in the following AE categories will be summarized for each treatment group by system organ class (SOC), high level term (HLT) and preferred term (PT):

- TEAEs
- drug related TEAEs.

The number and percentage of subjects with TEAEs in the following AE categories will be summarized by SOC and PT:

- serious TEAEs,
- drug related serious TEAEs,
- TEAEs leading to permanent discontinuation of study drug,
- drug related TEAEs leading to permanent discontinuation of study drug,
- TEAEs that equal to or exceed a threshold of 5.0% in any treatment group (threshold is based on PT).

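### Exposure-adjusted AE rates (SAP 6.5.1) count events to 21 days after the last dose but divide by exposure ending at the last dose, and the numerator is not defined row by row

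*SAP*

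**What the plan says.** SAP 5.1 makes "Frequency and severity of AEs" part of the primary safety endpoint. SAP 6.5.1 defines treatment-emergent AEs as "AEs that occurred on or after first dose of study drug and 21 days after the last dose of study drug". Protocol 7.6.1 gives the same 21-day limit, and its second wording, which runs to the last scheduled procedure, also extends past the last dose.

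The SAP 6.5.1 overview lists, for most categories, both a count of events and a count of women. It then adds a second overview, meant to adjust for differences in "durations and the potential differential dropout rates between the treatment groups". In that table an "exposure adjusted incidence rate (per 100 subject-years) for the above AE categories will be summarized". Only one denominator is given: "The total subject-years of exposure is calculated as the sum over subjects of the total duration of exposure divided by 365.25". The formula sums (ld − fd + 1)/365.25, where fd and ld are the first and last dose dates.

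SAP 6.5 limits most safety data so that "only data up to one day after the last dose date will be considered for the analyses", but it exempts AEs and follow-up visit data. SAP 6.10.1 exempts AEs in the same way.

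**The concern.** A rate per 100 subject-years is interpretable only if events and time come from the same period. Here up to 21 days per woman can add events but no time, and no other rule in the SAP or protocol closes the gap. Those days are observed: AEs are collected for 21 days after the last dose (Protocol 5.8.1), and women who stop early also have a visit three weeks later (Protocol 2.2.1).

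The second issue is the rows that count women. The SAP does not write out the numerator of the rate. It promises the rate for the categories just listed, which include counts of women, and it supplies one total exposure. Read that way, a woman keeps adding time to the denominator after her first event, so the result is not a first-event incidence rate.

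This is the only AE summary in the SAP that adjusts for time on drug and dropout, so its rates should be what they are labelled to be.

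**Working it through.** The documents state no exposure-adjusted rate, so there is no figure of the plan's own to reproduce.

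**Inputs from the documents**
- Planned treatment: 52 weeks = 52 × 7 = 364 days (Protocol Synopsis).
- Event window: to last dose + 21 days. Denominator: to last dose (both SAP 6.5.1).
- Phase 2b completion: 84% on placebo and 80% on fezolinetant (Protocol 2.2.2), so dropout of 16% and 20%.

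**Assumptions, not in the documents**
- h, the off-drug hazard relative to the on-drug hazard: 0 to 1.
- q, the share dropping out: 10% to 40%. m, mean days on drug in dropouts: 60 to 180.
- Constant hazard, and 50% as an example of a common category.

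The true h is unknown. It need not be zero: in phase 2b, transaminase elevations were reported "in 7 subjects between 4 and 8 weeks after start of study treatment and in 2 unique subjects during study follow-up". The 4 to 6 hour half-life (Protocol 1.3.2) makes a value below 1 plausible for drug-related events.

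**1. Event-count rows, one completer.** Overstatement = (364 + 21h)/364.
- h = 0: 1.000
- h = 0.5: 374.5/364 = 1.029
- h = 1: 385/364 = 1.058

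For 580 completers the denominator is 580 × 364/365.25 = 578.0 subject-years, against 580 × 385/365.25 = 611.4 over the event window.

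**2. Event-count rows, whole arm, dropouts fully followed.** Overstatement = [(1 − q)(364 + 21h) + q(m + 21h)] / [(1 − q)364 + qm].
- h = 1, q = 0.10, m = 180: (346.5 + 20.1)/(327.6 + 18.0) = 366.6/345.6 = 1.061
- h = 1, q = 0.40, m = 60: (231.0 + 32.4)/(218.4 + 24.0) = 263.4/242.4 = 1.087
- h = 0.5, same ranges: 1.030 to 1.043
- h = 1, dropouts with no off-drug follow-up: 1.043 to 1.057

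**3. Event-count rows, between arms** (equal true rates, h = 1, full follow-up, m from 60 to 180).
- 16% vs 20% dropout: 1.001 to 1.003
- 10% vs 20%: 1.003 to 1.006
- 10% vs 40%: 1.011 to 1.022

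**4. Subject-count rows over total exposure, completers.** Ratio to the first-event rate = (p/364) / [−ln(1 − p)/(364 + 21h)].
- p = 50%, h = 0: 0.5/0.693 = 0.721, or 28% too low
- p = 50%, h = 1: (0.5/0.693) × (385/364) = 0.763, or 24% too low
- p = 5%: 0.975 (h = 0) to 1.031 (h = 1)

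The two effects pull in opposite directions in these rows and cancel near 11% incidence when h = 1.

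**5. Subject-count rows, between arms, equal hazards, 50% incidence in completers.** Rate = [(1 − q)pc + q·pd] / [(1 − q)364 + qm], where pc and pd are the risks over 364 + 21h and m + 21h days. Example with h = 0 and m = 60, so pd = 1 − 0.5^(60/364) = 0.108:
- 40% dropout: (0.300 + 0.043)/242.4 = 0.343/242.4
- 10% dropout: (0.450 + 0.011)/333.6 = 0.461/333.6
- Adjusted ratio 1.025; crude ratio 0.343/0.461 = 0.74

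Over h from 0 to 1 and m from 60 to 180, the adjusted ratio is 1.025 to 1.053 for 10% vs 40% dropout, where crude percentages give 0.74 to 0.88. For 16% vs 20% it is 1.003 to 1.006.

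**The case against.** The strongest reply is that little depends on this. The table is descriptive, no test uses it, and the crude AE tables, which also report the primary AE endpoint, are unaffected. That stands, and it limits how much weight the point carries.

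A reader might go further in four ways that the documents do not support.

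- **That the SAP expressly divides counts of women by total exposure.** It does not. Later in 6.5.1 the word categories is used for types of event, so the rates could be meant for event counts only. Total exposure would then be an acceptable kind of denominator, and only the window would be at fault. The subject-row reading is the natural one, because the list contains those rows and a single denominator is given. What is certain is that the numerator is unspecified.
- **That the table would hide a real difference by pulling a hazard ratio toward 1.** With equal follow-up the denominator cancels and what remains is the ordinary risk ratio, which the crude percentages show too. The SAP plans no ratio for this table.
- **That the adjustment fails in its purpose.** Step 5 shows that it removes most of the dropout bias in crude percentages; a small residue remains.
- **That phase 2b shows off-drug events to be as frequent as on-drug ones.** Nine women cannot establish that. One follow-up case, which "occurred at the follow-up visit, 3 weeks after the last dose", was considered unlikely to be related to study drug (Protocol 2.2.2).

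The rows also differ. The mismatch hardly touches AEs leading to permanent discontinuation, and deaths have no stated window.

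**Conclusion.** The window mismatch is real and follows directly from the text of SAP 6.5.1. Event-count rates are too high by 0% to 5.8% for a 364-day completer, and by about 6% to 9% at arm level under equal off-drug hazard, full follow-up and 10% to 40% dropout. They are overstated less if fewer events start off drug. Distortion between arms is small: 0.1% to 0.3% at the phase 2b dropout figures and up to about 2% at 10% vs 40%.

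The subject-row problem rests on a reading of unspecified text. On that reading, and with a constant hazard, common categories fall well below the first-event rate and uncommon ones barely change. The residual between-arm effect is under 1% at phase 2b dropout and 2.5% to 5.3% at 10% vs 40%.

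This does not put the primary AE results in doubt. It is a definition to correct before database lock, because the table would otherwise not report the rate that its label promises.

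**What to change.** Change the exposure-adjusted table only.

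1. **Match the periods**, by one of two routes.
   - Keep the protocol definition of treatment-emergent AEs and add each woman's actual follow-up after the last dose, up to 21 days, to her time at risk. If no events start off drug, this dilutes the on-drug rate by up to 5.5% for a completer (364/385 = 0.945).
   - Restrict both events and time to first dose through last dose + 1 day, the cut-off that SAP 6.5 already applies to other safety data. This gives an on-drug rate but drops events with onset 2 to 21 days after the last dose from this table. It needs a footnote that counts differ from the crude overview.
2. **State the window for deaths** explicitly under either route.
3. **Write out the numerator for each row.** In subject-count rows, end each woman's time at risk at her first event in that category. In event-count rows, keep total time at risk.

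The crude AE tables stay as planned. The cost is SAP wording, table shells and a first-event date per category, with no new data. Event-count rates and those for uncommon categories change slightly; subject-count rates for common categories rise more, as step 4 shows.

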6.5.2 Clinical Laboratory Evaluation

Quantitative values evaluated by the central laboratory including hematology, biochemistry, and urinalysis will be summarized using mean, standard deviation, minimum, maximum and median by treatment group at each analysis visit. Additionally, a within-subject change will be calculated as the post-baseline measurement minus the baseline measurement and summarized in the same way. Each laboratory result will be classified as low (L), normal (N), or high (H) at each visit according to the laboratory supplied reference ranges.

Frequency tabulations of qualitative clinical laboratory variables (urinalysis) will be presented for each treatment group at each visit.

Number and percentage of subjects with platelets $< 150 \times 10^{9}$ /L will be separarely summarized for each treatment group.

For hematology and biochemistry shift tables will be presented for each treatment group:

Summary shifts of reference range changes from baseline to worst finding during the treatment period (shift from normal or high to low, shift from normal or low to high, categorized increase [shift from low to normal or from normal to high], categorized no change [value stays in the same reference range], categorized decrease [shift from high to normal or from normal to low]).

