7.6.2 Laboratory Assessments

For quantitative laboratory measurements descriptive statistics will be used to summarize results and change from baseline for subjects in the SAF by treatment group and time point.

Shifts relative to normal ranges from baseline to each time point during treatment period in lab tests will also be tabulated. Laboratory data will be displayed in listings.

Number and percentage of subjects with platelets $< 150 \times 10^9/L$ will be separately summarized for each treatment group. The liver safety assessments will be summarized by the categories below based on the measurements from ALP, ALT, TBL, AST and their combination. These parameters will be based on measurements from a central laboratory.

The subject's highest value during the treatment period will be used.

- $ALT > 3 \times ULN, > 5 \times ULN, > 10 \times ULN, > 20 \times ULN$
- $AST > 3 \times ULN, > 5 \times ULN, > 10 \times ULN, > 20 \times ULN$
- $ALT \text{ or } AST > 3 \times ULN, > 5 \times ULN, > 10 \times ULN, > 20 \times ULN$
- $ALP > 1.5 \times ULN$
- $TBL > 2 \times ULN$
- $(ALT \text{ or } AST > 3 \times ULN) \text{ and } TBL > 2 \times ULN$
- $(ALT \text{ or } AST > 3 \times ULN) \text{ and } ALP < 2 \times ULN \text{ and } TBL > 2 \times ULN$

The last 2 criteria where 2 or more parameters are evaluated will be with the measurements on the same day or up to 1 day apart.

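### The SAP laboratory shift table leaves low-to-high and high-to-low moves out of its increase and decrease rows, gives no direction for the worst finding, and omits the by-time-point shifts planned in the protocol.

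*SAP*

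**What the plan says.** SAP 6.5.2 describes the table for hematology and biochemistry as "Summary shifts of reference range changes from baseline to worst finding during the treatment period". It then lists five rows:

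- two directional rows: "shift from normal or high to low, shift from normal or low to high"
- an increase row and an unchanged row: "categorized increase [shift from low to normal or from normal to high], categorized no change [value stays in the same reference range"
- a decrease row: "categorized decrease [shift from high to normal or from normal to low"

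The same section also provides that "Each laboratory result will be classified as low (L), normal (N), or high (H) at each visit according to the laboratory supplied reference ranges", but it specifies no tabulation of shifts by visit.

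Protocol 7.6.2 has a different time basis: "Shifts relative to normal ranges from baseline to each time point during treatment period in lab tests will also be tabulated".

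Laboratory tests are a secondary safety endpoint (Protocol 2.3.2, SAP 5.2). Platelets below 150 × 10⁹/L (SAP 6.5.2) and the liver categories (SAP 6.5.2.1) are summarized separately from the shift table.

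**The concern.** There are three separate weaknesses.

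First, increase, no change and decrease read as if together they account for every woman, but the two-step moves belong to none of them.

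Second, the worst finding is singular and has no direction. For a test such as potassium, glucose or leukocytes, both a low and a high value can be abnormal, and two programmers could build different tables from the same sentence.

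Third, the protocol plans shifts at each time point, and the SAP keeps only one comparison over the whole treatment period.

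Outside the liver categories and the platelet threshold, this table is the only planned view of hematology and biochemistry against the reference range that takes the baseline category into account. What is at stake is whether its rows add up, whether it can be reproduced, and whether a reader can see when women leave the normal range.

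**Working it through.** **1. Which combinations each row covers.** There are 3 baseline categories and 3 on-treatment categories (L, N, H), so 3 × 3 = 9 combinations. Each is placed in the rows exactly as SAP 6.5.2 words them.

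| Baseline → on treatment | Directional row | Increase / no change / decrease |
|---|---|---|
| L → L | none | no change |
| L → N | none | increase |
| L → H | to high | **none** |
| N → L | to low | decrease |
| N → N | none | no change |
| N → H | to high | increase |
| H → L | to low | **none** |
| H → N | none | decrease |
| H → H | none | no change |

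Increase, no change and decrease cover 2 + 3 + 2 = 7 of 9. The five rows together cover 9 of 9, because L → H and H → L sit in the directional rows. If L → H is added to increase and H → L to decrease, the three rows cover 3 + 3 + 3 = 9 of 9 without overlap, given one on-treatment category per woman.

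**2. What a single worst finding would do.** Take a woman who is normal at baseline with both a low and a high value on treatment. If low is taken as worst, she counts in the to-low row and in decrease. If high is taken, she counts in the to-high row and in increase. Either way the other abnormality is not counted.

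Nothing else in the SAP settles the choice. SAP 6.5.2.1 names the highest value for liver tests, but 6.5.2 has no such statement. The rule for several observations in SAP 6.10.1 picks a value within a visit window and does not define the worst value across the treatment period.

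**3. How many women that could affect.** The documents give no within-woman correlation, so this part rests on assumptions: normally distributed values, limits at ±1.96 (a central 95% range), equal correlation between all visits, no treatment effect, and 13 full-panel on-treatment visits (every 4 weeks from Week 4 to Week 52; Week 2 is liver biochemistry and INR only, Protocol Table 1, footnote i). Simulating 400,000 women gives, per analyte:

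| Correlation | Low at least once, if normal at baseline | Both low and high on treatment, per 580 | Baseline low with a later high, or the reverse, per 580 |
|---|---|---|---|
| 0.3 | 0.21 | 5.2 (0.9%) | 0.9 |
| 0.5 | 0.16 | 0.4 (0.07%) | 0.07 |
| 0.7 | about 0.10 | about 0 | about 0 |

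By symmetry the share going high equals the share going low. At correlation 0.3 there are about 580 × 0.95 × 0.21 × 2 ≈ 231 shifts into an abnormal range per arm, so losing 5.2 is about 2%. At 0.5 it is 0.4 of 580 × 0.95 × 0.16 × 2 ≈ 176, or about 0.2%.

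**4. Time points.** SAP 6.10.1 sets 14 on-treatment laboratory windows, 13 of them for the full panel. Protocol 7.6.2 calls for a shift at each time point; SAP 6.5.2 reduces them to one comparison. Neither SAP 6.5.2 nor the list of changes in SAP 7.1 gives a reason. For the laboratory sections, that list mentions only a liver category added in 6.5.2.1. This step depends on no assumption about the data.

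**The case against.** The strongest reply is that the table already answers the safety question. The two directional rows isolate moves into an abnormal range, and they include low-to-high and high-to-low. A reader might infer that the largest shifts vanish and that women moving to an abnormal range are therefore undercounted. The documents do not support that: all nine combinations are covered once the directional rows are read. This part of the reply stands in full.

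A reader might also infer that the SAP forces one worst value per woman into every row. It does not. Separate rows for shifts to low and to high could be filled from each woman's minimum and maximum. What remains is that the SAP does not say so, and the singular wording allows the other reading.

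On time points, the SAP keeps the L/N/H classification and the summaries of values and changes at each visit, and SAP 6.1 leaves table formats to specifications that are not among these documents. So no data are lost, and the table could be built from planned variables. But summaries of means and changes do not show when women cross a reference limit, and a table format document is not the place for an unexplained departure from the protocol.

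That the increase row pools recovery (low to normal) with deterioration (normal to high) is a presentation convention, not an error.

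**Conclusion.** The point holds, and it is minor. Three things are established from the text alone: the increase, no-change and decrease rows cover 7 of 9 combinations; the worst finding has no stated direction for two-sided tests; and the by-time-point shifts of Protocol 7.6.2 are absent from the SAP without a stated reason.

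The numerical effect of the first two is small. Under the single-value reading, 0 to 5 women per analyte per arm of 580 would lose one shift, and the upper figure needs an assumed correlation as low as 0.3. At most about 1 more per arm would make a two-step move and fall outside the three net-direction rows, and she would normally still appear in a directional row. The 10% to 21% of women who go low at least once shows how much the rows are used; it should not be read as the share of shifts lost. The third omission touches every analyte in the table, but it concerns presentation of data that are already classified.

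These are descriptive summaries of a secondary safety endpoint. No primary endpoint or treatment comparison depends on them, and the liver categories and the platelet threshold are unaffected.

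**What to change.** In SAP 6.5.2:

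1. Define increase as any upward category move and decrease as any downward one, so that low-to-high and high-to-low are included. State which on-treatment value feeds these rows, since they add up to all women only with one category per woman.
2. Fill the shift-to-low row from each woman's lowest on-treatment value and the shift-to-high row from her highest, so that a woman with both is counted in both.
3. Add the shift from baseline at each analysis visit, using the L/N/H classification already planned. Alternatively, record the departure from Protocol 7.6.2 with a reason.

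The cost is a few lines of SAP text, standard table programming and a longer table set. No new data are needed.
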